### Study Synopsis

Protocol #	CLN 0827
Study Title	Evaluation of the Efficacy and Safety of a thermal fractional skin treatment system (Tixel®) for the treatment of facial and/or scalp actinic keratoses
Study Device	Tixel C (by Novoxel)
Device Description	Tixel technology is a thermal fractional skin treatment system powered by Thermo-Mechanical Action technology. Tixel employs a hot titanium tip which transfers direct heat to the skin. The proprietary tip is constructed of biocompatible temperature resistant titanium alloy cover mounted on gold plated copper base. The tip consists of an array of tiny pyramids which are heated to a temperature of 400°C. The apex of the pyramids transfers thermal energy to skin by very brief controlled contact time.
Study Design and Duration	
Single-center, Prospective, Open Label, with Before-After Study Design.
 
Up to 25 subjects will be enrolled to the study to provide at least 20 evaluable subjects. Subjects will be examined to determine the severity and extent of actinic keratoses.
 
All subjects will undergo 1-3 treatments (determined by the investigator assessment), 3-4 weeks apart.
 
Follow-up visits will be performed after the last treatment visit: 4 weeks (±7 days) and 12 weeks (±7 days).
 
The inclusion criteria would be mild to moderate thickness confluent actinic keratoses located to scalp and/or face.
 
Each subject will participate in the study for up to 20 weeks.
 
Total study duration is estimated to be up to 12 months from enrollment of the first subject until last subject visit (including FUs).

Investigational Treatment	This is a non-invasive thermo-mechanical treatment to the scalp and/or face using the Tixel technology. The handpiece will be pressed gently onto the scalp/facial skin while transferring heat in a predetermined setting.
Objectives	
Primary objective
 
To evaluate the efficacy of the Tixel technology (device) for the treatment of facial and/or scalp actinic keratoses.
 
Secondary objectives
 
 
• To evaluate procedure-related adverse reactions.
 
• To evaluate Subject's subjective downtime assessment.
 
• To Evaluate the pain of the treatment.
 
• To Evaluate the subject's satisfaction.
 

Study synopsis.


Study Population
	
Up to 25 subjects will be enrolled to the study to provide at least 20 evaluable subjects presenting with mild to moderate thickness confluent actinic keratoses located to scalp and/or face who wish to treat their condition by using a non-invasive thermo-mechanical treatment.

Inclusion Criteria:
	
 
1. Male and female, age 18-80 years old.
 
2. Skin Phototype I-VI.
 
3. Subject has mild to moderate thickness confluent AKs on his/her scalp and/or face.
 
4. Subject is willing and able to comply with protocol requirements and all study visits.
 
5. Subject has provided written informed consent.
 


Exclusion Criteria:
	
General
 
 
1. Any patient who has undergone tanning during the 4 weeks prior to any treatment session and/or any patient who plans to undergo tanning during the 4 weeks following any treatment session (patients who may be exposed to the sun for short periods of time occasionally are not contra-indicated as long as they apply a high SPF sunscreen (>50).
 
2. Current active Herpes Simplex infection.
 
3. Current skin cancer, malignant sites and/or advanced premalignant lesions or moles in the treatment area.
 
4. An impaired immune system condition or use of immunosuppressive medication.
 
5. Collagen disorders, keloid formation and/or abnormal wound healing.
 
6. Any patient who takes or has taken any medications (including via topical application), herbal treatment (oral or topic), food supplements or vitamins, which may cause fragile skin or impaired skin healing during the last 3 months.
 
7. Any patient who has used oral retinoids within 6 months prior to treatment or less.
 
8. Any patient who has a history of bleeding coagulopathies.
 
9. Any patient who has tattoos or permanent makeup in the treated area.
 
10. Any patient who has burned skin, blistered skin, irritated skin, or sensitive skin in any of the areas to be treated.
 
11. Women who are pregnant (as determined by self-reporting), lactating, or less than 3 months post-delivery, possibly pregnant or planning a pregnancy during the study period.
 
12. Currently participating in or recently participated in another clinical trial (within the last 30 days).
 
 
Previous/Current AKs Treatments  Subject underwent prior treatments for actinic keratoses including:

Study synopsis.

	
13. Prior treatment with ablative laser, any laser or photo-dynamic therapy 3 months prior to enrollment.
 
14. Any cryotherapy or electrodesiccation 6 weeks prior to enrollment.
 
15. Systemic retinoid therapy within 6 months prior to enrollment, topical treatment with 5-Fluorouracil cream and/or imiquimod cream and/or diclofenac gel 6 months prior to enrollment.
 
16. Prior treatment with Tixel.
 
Treatment or treatment area related:
 
17. Face cannot be treated due to dermal disorder other than AKs, such as infection, surgical treatment etc.
 
Medical Conditions
 
18. Subject has a systemic disease manifested by AKs (e.g. immune suppression).
 
19. Significant systemic illness.

Study Evaluations
	
Efficacy:
 
Lesion count by the investigator, confirmed and documented using Standardized high-resolution digital photography of the treatment area (before and after marking the present actinic keratoses using a washable eyeliner) will be performed for each subject at baseline (before), at each treatment visit (prior to the treatment session) and at 4 and 12 weeks FU visits.
 
Safety:
 
 
• Skin safety throughout the study as determined by the investigator on site before and after treatments as well as by examining the post-treatment occurrences of complications and adverse events.
 
• Procedure related pain by VAS of 0-10 where a higher score indicates greater pain.
 

Primary Efficacy Endpoint:
	
The overall mean percentage reduction in actinic keratoses lesion count performed by the investigator manually, confirmed and documented using photograph images taken at baseline and at 12 weeks follow-up visit (or 12-weeks post last treatment if less than 3 treatments were done) (before and after marking the present actinic keratoses using a washable eyeliner) calculated as the relative change from baseline at 12 weeks. New lesions which were not existed in baseline will not be counted.


Secondary Efficacy Endpoints:
	
 
• The mean change in actinic keratoses lesion count, performed by the investigator manually, confirmed and documented using photograph images, from baseline at 4 and 12 weeks follow-up visit.
 
• The overall mean percentage reduction in actinic keratoses lesion count performed by the investigator manually, confirmed and documented using photograph images taken at baseline and at 4 weeks follow-up visit (before and after marking the present actinic keratoses using a washable eyeliner) calculated as the relative change from baseline at 4
 

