## **Efficacy Analysis**

### ***Primary endpoint***

The overall mean percentage reduction in AK lesion count performed by the investigator manually, confirmed and documented using photograph images taken at baseline and at 12 weeks follow-up visit calculated as the relative change from baseline at 12 weeks will be calculated along with 95% confidence interval.

The Paired T-test or Signed rank test for two means (paired observations) (as is appropriate) will be applied for testing the statistical significance of the percentage reduction in in actinic keratosis lesion count from baseline at week 12 (compared to 50%).

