## **Safety Analysis**

- Subject assessment of pain, as measured by a VAS score, associated with treatments will be tabulated and summarized *via* descriptive statistics.
- Skin safety throughout the study as determined by the investigator by examining the post-treatment occurrences of complications and adverse events.
- Adverse events will be coded using the Medical Dictionary for Regulatory Activities (MedDRA, most updated version) terminology and presented in tables by System Organ Class (SOC) and Preferred Term (PT).

Study synopsis.

- Adverse events (AE) will be presented by seriousness, severity, and relation to treatment.
- Concomitant medications entered into the database will be coded using the World Health Organization (WHO) Drug Reference List, which employs the Anatomical Therapeutic Chemical classification system.

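### The plan has no rule for lesion counts taken after non-study AK treatment, so a baseline lesion cleared by another therapy before week 12 counts as a device reduction

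*Combined protocol and SAP*

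**What the plan says.** **Limits on other AK treatments (Study Synopsis, Exclusion Criteria 13-15).** All of them look back from enrollment:
- Laser and photodynamic therapy: "Prior treatment with ablative laser, any laser or photo-dynamic therapy 3 months prior to enrollment".
- Cryotherapy and electrodesiccation: "Any cryotherapy or electrodesiccation 6 weeks prior to enrollment".
- Topical agents: "topical treatment with 5-Fluorouracil cream and/or imiquimod cream and/or diclofenac gel 6 months prior to enrollment". The same criterion sets a six-month window for systemic retinoids.

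**Nearby criteria.** Criterion 7 is timed to treatment but still looks back: "Any patient who has used oral retinoids within 6 months prior to treatment or less". Criterion 6 concerns products "which may cause fragile skin or impaired skin healing during the last 3 months". Criterion 1 does look forward, but for tanning: "any patient who plans to undergo tanning during the 4 weeks following any treatment session".

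**Endpoint.** The primary measure is the percentage reduction in the investigator's lesion count, "calculated as the relative change from baseline at 12 weeks will be calculated along with 95% confidence interval" (Efficacy Analysis, Primary endpoint). The endpoint definition sets aside lesions that were not there at baseline. It has no other rule on attribution.

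**Analysis sets.** Primary efficacy uses the per-protocol set, defined by receipt of the full treatment session and 3-month photographs. The full analysis set is supportive and needs one device treatment.

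**Recording.** Under Safety Analysis, "Concomitant medications entered into the database will be coded using the World Health Organization (WHO) Drug Reference List". Disposition of Subjects plans a listing of protocol deviations and exclusions. Handling of Missing Data rules out imputation.

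**The concern.** The endpoint compares two counts and attributes the whole difference to the device. If a baseline lesion is frozen or treated with a topical agent between the first device session and week 12, it is gone at week 12 whatever removed it. The plan neither separates that lesion nor sets the subject aside.

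In a controlled trial, outside treatment would occur in both arms and could partly cancel. Here there is one unblinded arm and a fixed 50% threshold, so nothing offsets it. Because new lesions are not counted, outside clearance can only raise the measured reduction. The primary result, the 4-week result and the three responder bands are all exposed.

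**Working it through.** **1. Does any provision catch the case?** Take a subject who has baseline lesions treated elsewhere after the 4-week visit.
- Criteria 13-15 do not apply: their windows closed at enrollment.
- Criteria 6 and 7 are eligibility criteria on skin healing and oral retinoids. They do not reach cryotherapy or photodynamic therapy during follow-up.
- The per-protocol set keeps the subject, who has had the treatment and has the photographs. The full analysis set keeps the subject too.
- Medication coding may pick up a topical agent, for safety reporting. Cryotherapy and electrodesiccation are procedures, not medications.
- The deviation listing would include the subject only if other AK treatment were defined as a deviation, which the text does not do.
- The no-imputation rule is not triggered, because the week-12 count exists.

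**2. Time exposed.** From the schedule in the Study Synopsis: one session plus 12 weeks is 12 weeks. Three sessions 3-4 weeks apart plus 12 weeks is 2 × 3 + 12 = 18 to 2 × 4 + 12 = 20 weeks. The part after the 4-week visit is 12 − 4 = 8 weeks.

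**3. Yardstick.** Sample Size Estimation expects 58% against a threshold of 50%, a gap of 8 points, with n = 20 and SD 20. The stated half-width of 8 does not reproduce: 1.96 × 20/√20 = 8.77. That is a separate matter. The 8 points serve here only as the plan's own distance from expected result to threshold.

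**4. Size of the bias (assumption; no rate is given).** Let f be the fraction of subjects treated elsewhere, and c the share of their baseline lesions that this removes and that would otherwise still be present at week 12. The mean rises by 100 × f × c points. c cannot exceed the share left after the device: at a 58% reduction that is 100 − 58 = 42%.

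| f | c | Points added |
|---|---|---|
| 5% (1 of 20) | 30% | 1.5 |
| 10% (2 of 20) | 30% | 3 |
| 20% (4 of 20) | 30% | 6 |

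**5. One subject.** Ten baseline lesions, 4 cleared by the device and 3 by cryotherapy: scored (4 + 3)/10 = 70% instead of 4/10 = 40%. The subject moves from the 26-50% band to the 51-75% band.

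**6. Effect on the comparison with 50%.** Simulation of 100,000 trials: n = 20, device-only reduction normal with mean 50% and SD 20, capped at 100%, two-sided 95% t interval. In k subjects, half or all of the remaining lesions are cleared elsewhere. Each such subject adds about 25/20 = 1.25 or 50/20 = 2.5 points to the mean.

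| k | Chance that lower limit exceeds 50%, half cleared | Same, all cleared |
|---|---|---|
| 0 | about 2.6% | about 2.6% |
| 1 | about 4% | about 5% |
| 2 | about 7% | about 9% |
| 3 | about 10% | about 17% |

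**The case against.** **The document may be incomplete on this point.** The supplied text is a synopsis with an analysis plan. It has no section on visit procedures or concomitant treatment, and it refers to medications entered in a database without describing their collection. A reader might infer that the study leaves outside AK treatment unrestricted. The documents do not support that; they show only that the supplied text is silent. What stands is that the analysis plan has no rule for counts after such treatment. A prohibition elsewhere would not say how to score a subject who broke it.

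**Motive.** A reader might infer that the washouts show the sponsor's view that these therapies alter lesion counts. No reason is given, and the windows fit skin-safety washouts equally well. The point does not depend on the motive.

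**Likelihood.** A reader might infer that poor responders will seek treatment elsewhere. They have more lesions left to treat, but no passage gives a rate or says that they do. Subjects enroll wanting this treatment, and up to three sessions are available at the investigator's assessment. This objection stands: occurrence is possible, not shown.

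**Recording.** Topical agents may already be captured as concomitant medications, and a deviation listing is planned. This also stands: the clear recording gap is for procedures.

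**Choice of rule.** Counting what is present at week 12 regardless of other treatment is a recognised alternative, and scoring treated lesions as not cleared is conservative. That is a reason to report both, not to leave the choice until the data are seen.

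**Conclusion.** The concern holds for the supplied text. Followed as written, the count rule credits the device with any baseline lesion that non-study therapy clears before week 12, and in this single-arm design any such bias favours the device.

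Its size is unknown. Under the assumed f and c it runs from 1.5 points (one subject of 20) to 6 points (four of 20), against an 8-point gap. A reader might infer that the bias would use up the whole gap. That would need, for example, f = 20% and c = 40%, since 100 × 0.20 × 0.40 = 8. With 42% of lesions left at the expected reduction, this means nearly all remaining lesions cleared elsewhere in four of 20 subjects, and nothing in the documents supports it. If no outside treatment occurs, the bias is zero.

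**What to change.** 1. **Record.** At each visit, record non-study AK treatments, including procedures, with date and site. List affected subjects alongside the deviations planned in Disposition of Subjects.
2. **Score.** In Efficacy Analysis, for the primary and the count-based secondary endpoints, score any baseline lesion that receives non-study AK treatment after the first device session as not cleared at all later counts. For field-applied therapy, score as not cleared every baseline lesion in the treated field that was still present at the last count before it.
3. **Clarify.** State that this is a scoring rule for observed counts, not imputation, so that it does not conflict with Handling of Missing Data.
4. **Sensitivity.** Report the count regardless of other treatment as a sensitivity analysis.

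In the ten-lesion example, the main analysis would give 40% and the sensitivity analysis 70%.

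**Cost.** A short analysis rule, an entry on the visit form and a listing. Treated lesions must be identified on photographs that are already planned. If outside treatment occurs, the reported reduction may be slightly less favourable, and it will be somewhat conservative for lesions that the device would have cleared later. This changes recording and scoring only; no rule is proposed on whether such treatment is allowed.

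### Exclusion 17 tests only the face, although the trial enrols and treats scalp and/or face; the item should refer to the treatment area

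*Combined protocol and SAP*

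**What the plan says.** The Study Synopsis is consistent about where the device is used. Under Investigational Treatment: "This is a non-invasive thermo-mechanical treatment to the scalp and/or face using the Tixel technology". Inclusion 3 has the same scope: "Subject has mild to moderate thickness confluent AKs on his/her scalp and/or face". A candidate with lesions on the scalp alone is therefore eligible.

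Exclusion 17 stands alone under the heading "Treatment or treatment area related", but its text is limited to one of the two sites: "Face cannot be treated due to dermal disorder other than AKs, such as infection, surgical treatment etc". No matching item names the scalp.

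Other exclusions that depend on the skin to be treated are worded without naming a site. Item 3 reads "Current skin cancer, malignant sites and/or advanced premalignant lesions or moles in the treatment area" and item 10 reads "Any patient who has burned skin, blistered skin, irritated skin, or sensitive skin in any of the areas to be treated". Item 9, on tattoos and permanent makeup, likewise refers to the treated area.

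**The concern.** Eligibility is applied and monitored against the written text. For a scalp-only candidate, item 17 as written looks at a site that will not be treated and ignores the one that will. It can therefore go wrong in both directions: a person with a scalp condition of the kind the item describes does not meet it, and a person whose only problem is on the untreated face does.

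What is at stake is consistent eligibility and safety at scalp sites. The Device Description gives a tip temperature of 400°C. The plan treats infection or surgical treatment that makes the face untreatable as a reason for exclusion, says nothing equivalent for the scalp, and gives no reason for the difference.

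**Working it through.** No arithmetic applies: the plan gives no figure for this point, and the point depends on no variance, effect size, dropout rate or sample size. The check compares item 17 with the treated sites and then asks whether another exclusion closes the gap.

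**Step 1. Scope.** Treated sites (Investigational Treatment): scalp and/or face. Eligible sites (Inclusion 3): scalp and/or face. Heading over item 17: treatment area. Text of item 17: face only. The item is narrower than all three.

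**Step 2. Item 17 applied literally to candidates who have a disorder, other than AK, that prevents treatment of the affected site.**

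- Face-only candidate, disorder on the face: excluded. The item works.
- Scalp-only candidate, disorder on the scalp: not excluded by item 17.
- Scalp-only candidate, disorder on the face: excluded, although the face is not to be treated.
- Candidate with lesions on both sites, disorder on the scalp: not excluded by item 17.

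**Step 3. Do other exclusions cover the scalp?** In part.

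- Item 2 has no site limit: "Current active Herpes Simplex infection". It covers one infection only.
- Item 3 covers cancer, malignant sites, advanced premalignant lesions and moles in the treatment area, scalp included.
- Item 5 has no site limit: "Collagen disorders, keloid formation and/or abnormal wound healing".
- Item 9 covers tattoos and permanent makeup at either site.
- Item 10 covers burned, blistered, irritated or sensitive skin at either site. Some infected or recently operated scalps would be caught here.
- Items 13 and 14 have no site limit, but they concern earlier AK treatment. They name laser, photodynamic therapy, cryotherapy and electrodesiccation; surgery is not among them.

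**Step 4. What is left.** At a scalp treatment site, three things that item 17 addresses for the face are not excluded by name: infection other than herpes simplex, surgical treatment, and other dermal disorders that do not fall under one of the items in step 3.

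**Step 5. The reverse error.** The third case in step 2 follows from the wording alone, and no other item undoes it.

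**The case against.** The strongest reply is that the intent is plain. The heading says treatment area, there is one centre, so different sites cannot read the item differently, and a sensible investigator would not refuse a scalp-only candidate because of a facial rash. Several other items already protect the scalp, and the Safety part of Study Evaluations has the investigator judge skin safety before and after treatments.

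Much of this stands. It rules out the broad statement that scalp disorders go unexcluded, because items 2, 3, 5, 9 and 10 exclude several. It also makes it likely that few candidates would be handled wrongly. It does not remove the defect. Enrolling or refusing someone on an inferred meaning departs from the written criterion, and the skin check at treatment is not an eligibility rule.

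Three stronger readings are tempting, and the documents support none of them.

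- A reader might take the whole scalp-only share of the 25 subjects as the number affected. The documents do not give that share, and it would count everyone for whom the item looks at the wrong site. Only those who also have a relevant disorder could be misclassified.
- A reader might infer that each wrongly excluded candidate is lost from a small sample. A candidate refused at screening was never enrolled. Disposition of Subjects reports screening failures separately from enrolled subjects, and another candidate can be screened.
- A reader might infer that other scalp dermatoses would be miscounted as AK in the primary endpoint. Item 17 applies only where the site cannot be treated, so a treatable dermatosis that resembles AK is outside it on the face as well, and would stay outside it after rewording.

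**Conclusion.** The point holds in a limited form. Item 17 names only the face, in conflict with its own heading, with Inclusion 3 and with the stated treatment sites. Followed literally, it leaves non-herpetic infection, surgical treatment and other dermal disorders at a scalp site not excluded by name unless another item catches them, and it excludes scalp-only candidates for a disorder of the untreated face.

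The number affected is probably small. It cannot be derived, because the documents give neither the share of scalp-only candidates nor the frequency of such disorders. The conclusion assumes only that eligibility is decided on the text as written. The sample size, the analyses and the error rates are untouched. The correction is worth making because the rule as worded is wrong for one of two treated sites, bears on safety there, and is cheap to put right.

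**What to change.** Reconcile item 17 with its heading and with Inclusion 3 by replacing the word face with the plan's own term, treatment area, and leave the rest of the item unchanged. This carries the plan's existing judgement to both sites it has chosen to treat and adds no new clinical rule.

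The cost is a few words in one criterion, with no extra procedure and no change to the analysis. The downside is that a few candidates with scalp disease would be screened out. In return, scalp-only candidates would no longer be refused for a facial disorder.
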